5.0 STUDY PROCEDURES

Subjects will be asked to complete a single research visit that will include the administration of a PSMA PET/CT and/or PET/MR exam. Subjects participating in the PET/MR imaging studies will be screened for contraindications to MRI and MR contrast agents using the standard UWCHC MR Safety screening form. A urine pregnancy test will only be done for women with childbearing capacity that are unable to verify their non-pregnancy status by self-report.

Aim 1. Biodistribution and radiodosimetry of PSMA-based ¹⁸F-DCFPyL in normal female controls or cancer patients (Up to 6 subjects for non-dosimetry and 6 subjects for radiodosimetry (dosimetry))

The research visit is estimated to take 2-3 hours, which includes approximately 60-120 minutes of scanning time. Subjects will be asked to fast for 4 to 6 hours prior to the research visit and to stay well hydrated.

The remainder of the time will be preparatory for the scanning. An IV will be placed to allow injection of the PET tracer during the exams.

Dosimetry Subjects: A less than 9 mCi dose of ¹⁸F-DCFPyL radiotracer will be administered by slow IV push after subject has been positioned in the PET/CT scanner. The subject's imaging session will include multi-pass PET scans to allow for normal organ and tumor biodistribution for a total of 5 PET scans from the vertex of skull through mid-thigh. Initial low-dose CT will be followed by 4 PET scans (PET1 through PET4) lasting approximately 60 to 75 minutes (depending on the height of the patient). The subjects will be allowed to leave the table to void between the fourth and fifth (PET5) PET scans. The fifth PET/CT scan (PET5) is obtained with another low-dose CT scan to allow for CT attenuation correction followed by the PET scan starting at approximately 90 minutes after radiotracer administration to last up to approximately 30 minutes (again, depending on the height of the patient). If the PET/CT takes less than 120 minutes, the subject may undergo a PET/MR, as time allows.

Dosimetry Subjects Only - Blood Collection:

- Blood (5mL Purple top at each time point) will be collected at 3 time points, after the completion of the 2nd, 4th and 5th PET passes on the PET dosimetry PET/CT protocol. Blood will be collected for the first 3 subjects and as needed for the remaining 3 subjects.
- Blood will be counted on a gamma counter after dilution to determine radioactivity on the same day as the scan. After radioactive decay overnight, blood will be disposed of as per routine biohazard.

Non-dosimetry subjects: An IV will be placed to allow injection of the PET tracer, MR gadolinium agent, and glucagon (if needed) during the exams. A less than 9 mCi dose of ¹⁸F-DCFPyL radiotracer will be administered by slow IV push outside the scanner, after which, the subject will be required to sit quietly for 60 minutes to allow for adequate biodistribution of the tracer. The subjects will then be placed in the PET/MR scanner and will remain in the scanner for up to 90 minutes. After which, the whole body (defined in this protocol as base-of-skull to mid-thigh) PET and MR images will be obtained to include images post-intravenous gadolinium contrast. Glucagon (0.5mg-1mg, IV) may be administered by IV prior to the MR imaging if excessive bowel movement is seen on initial images. Glucagon is known to diminish bowel motion and improve MR image quality.

Aims 2 & 3. Sensitivity, specificity, and accuracy values of PSMA-based ¹⁸F-DCFPyL PET and MR imaging and assessment of tumor burden (40 subjects with known or suspected gynecological cancer).

This research visit is estimated to take 2-3 hours. For subjects with gynecologic cancer, the subjects will be in the scanner for up to 90 minutes. The remainder of the time will be preparatory for the scanning. An IV will be placed to allow injection of the PET tracer, MR gadolinium agent, and glucagon (if needed) during the exams. Subjects will be asked to fast for 4 to 6 hours prior to the research visit and to stay well hydrated. There will be a 1-hour uptake period after IV administration of less than 9 mCi of ¹⁸F-DCFPyL radiotracer by slow IV push. After which, the whole body (defined in this protocol as base-of-skull to mid-thigh) PET and MR images will be obtained to include images post-intravenous gadolinium contrast. Glucagon (0.5mg-1mg, IV) may

be administered by IV prior to the MR imaging if excessive bowel movement is seen on initial images. Glucagon is known to diminish bowel motion and improve MR image quality.

A member of the study team will follow-up with all subjects approximately 1 to 3 days, by phone, after their PET/MRI or PET/CT exam to inquire about delayed side effects. If the subject is experiencing any late occurring side effects, they will be asked to return to the research clinic for a follow-up exam.

All PET and MR hardware are FDA approved as are the PET and MR sequences to be used.

Histopathological, Immunologic Staining and Image Correlation

We will correlate the final surgical pathology report with the images to determine if all sites of disease were seen on PSMA PET and MR imaging. In addition to this, we will identify very specific sites (eg. Left obturator node; Right ovarian mass; etc) for PSMA immunologic staining pre-operatively by review of the imaging between the radiologist and the gynecologic oncology surgeon and the surgeon will make every attempt to send these PSMA specimens labeled and separate from the other specimens obtain during surgery.

The surgical pathology specimens will be processed per routine clinical protocol. The same tissue blocks used for routine pathological evaluation will be used for the immunolabeling of the PSMA in the TRIP lab. After the clinical processing is complete, the pathologist will choose the appropriate tissue block(s) for immunolabeling, which consumes only a minute amount of tissue. This process will in no way compromise patient care.

Review of Medical Records

Medical records will be reviewed to obtain medical history including physical exams, medications, laboratory tests, imaging results and any other information related to the diagnosing, treatment, or outcomes of subjects diagnosis.

Remuneration

Subjects will receive \$100 as compensation for their participation in this study.

Study Withdrawal

Reasons for withdrawal or termination

Enrolled patients will be removed from the study in the following circumstances:

- The patient does not complete the imaging examinations per study protocol
- The subject withdraws consent
- Exclusion criteria are discovered after registration but prior to the research examinations
- The patient has a contrast reaction to the gadolinium based contrast agent utilized for the MRI
- The PI or co-investigators determine it is within the best interest of the subject to remove them from the research.

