| Exclusion Criteria | 
 • Women that are pregnant or breast feeding. • Age <18 |

| | |
|----------------------------|--|
| | 
 • Severe kidney dysfunction (GFR <30 mL/min/1.73m²) |
| Treatment Description | ¹⁸ F-DCFPyL whole body PET/CT or PET/MR scan |
| Study Procedures | 
 • ¹⁸F-DCFPyL whole body PET/CT imaging for dosimetry studies; PET/MR scan to achieve other aims • Review of relevant imaging and medical record information |
| Statistical Considerations | 
There are no formal hypothesis tests planned.
 
Our primary goals are to:
 
 1. Record the normal biodistribution and radiodosimetry of PSMA in the body 2. Record the frequency the normal fallopian tubes and ovarian are seen on high resolution MR imaging. 3. Record the distribution of PSMA in cancer tissue 4. Estimate the frequency with which PSMA PET and MR imaging and final IHC staining disagree in their classifications of presence of disease. We will classify each data point as either an agreement or disagreement between imaging findings and IHC staining. The proportion of disagreements across all time points will be estimated with an intercept-only GEE regression model that accounts for correlation among measures from the same patient. This proportion will be reported with a 95% confidence interval. The lower bound of this confidence interval will be used to help us decide whether this approach is worthy of future study. Based on this pilot study we plan to pursue further evaluation in larger more appropriately powered studies if the lower bound of the confidence interval excludes 20%, which is chosen as a guideline to determine whether the method shows promise. |

SCHEMATIC OF STUDY DESIGN

Subject Populations

1.0 PROJECT SUMMARY:

The purpose of our proposal is to use PSMA PET and multi-parametric MR imaging, to detect the presence of gynecological cancer cells in the body. Imaging evaluation would include the appearance of normal ovaries/fallopian tubes, and cancerous tissue on different MR sequences and the distribution of PSMA in normal and pathological tissues on PET images. To determine the accuracy of the PSMA PET imaging localization in malignant tissues, PSMA staining of surgical pathology specimens will be used as the reference standard.

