3.0 STUDY AIMS/STUDY OBJECTIVES

The primary outcome of this research is to evaluate whether a novel imaging approach using PSMA-based ¹⁸F-DCFPyL PET and MR imaging can accurately determine the presence or absence of cancer, the accurate distribution of cancer and the normal biodistribution of PSMA in the abdomen and pelvis on PET imaging. The reference standard for the PSMA localization in cancerous tissue will be histologic and immunologic correlation on the pathologic specimens obtained at the time of standard of care surgical resection for treatment of the gynecological cancer. Specific aims for this research include the following:

1. To establish the biodistribution and radiodosimetry of PSMA-based ¹⁸F-DCFPyL on PET imaging in normal female controls and in females with known or suspected cancer.
2. To determine the sensitivity, specificity, and accuracy values of PSMA-based ¹⁸F-DCFPyL PET and MR imaging in the detection of cancer in women with known or suspected gynecologic malignancy and differentiating cancerous tissue from non-cancerous tissue. The performance of PSMA-based ¹⁸F-DCFPyL PET imaging in the detection and localization of cancerous and non-cancerous tissue will be compared to the final surgical pathology reports and to the histological and immunostaining for PSMA positive cancerous tissue on pathology.
3. To determine the most accurate approach in assessing disease burden and location, assessment of tumor burden on both the PSMA-based ¹⁸F-DCFPyL PET and MR imaging

together, and then each modality separately will be performed and sensitivity, specificity, and accuracy values will be calculated.

4.0 RESEARCH DESIGN AND METHODS:

Subject population

Fifty-two subjects will be enrolled in this research, 12 healthy controls and 40 patients with known or suspected gynecologic cancer. Up to 6 subjects will be used for the dosimetry portion. Eligibility requirements include the following:

Inclusion Criteria for healthy female controls N=12 (includes up to 6 Dosimetry subjects)

1. Women with no suspected gynecological cancer
2. No contraindications for MR or PET imaging
3. Greater than or equal to 18 years of age
4. Scheduled to undergo a hysterectomy and/or salpingo-oophorectomy

Inclusion Criteria for female controls (Dosimetry)

1. Women with or without suspected gynecological cancer
2. No contraindications for MR or PET imaging
3. Greater than or equal to 18 years of age

Inclusion Criteria for gynecologic cancer patients N=40

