1. Women with known or suspected gynecological cancer
2. No contraindications for MR or PET imaging.
3. Greater than or equal to 18 years
4. Have had or are scheduled to undergo a hysterectomy and/or salpingo-oophorectomy

Exclusion Criteria

1. Women that are pregnant or breast-feeding.
2. Age <18
3. Inability to provide informed consent on their own behalf
4. Severe kidney dysfunction (GFR <30 mL/min/1.73m²)

Subject identification and recruitment

Healthy controls will be recruited from UWHC OB/Gyn and Women's Health and PATHS clinics through referrals and from posted flyers. Healthy controls may also be recruited from the Department of Radiology Volunteer Database (2017-0004). Potential subjects will either be introduced to the research by someone involved in their care or they will be required to contact

the study team by phone or email. Those interested in participating will be scheduled for an initial visit to learn more about participation and to complete the informed consent process.

Gynecologic Oncology staff will identify cancer patients who meet the eligibility criteria and will introduce them to this research opportunity. Those interested will be referred to a study team member who will review the purpose of the research as well as details about participation.

Informed Consent and Subject Information

The consent process will occur either on a day prior to or on the day of but prior to the administration of research procedures. During the COVID-19 pandemic, consent procedures will be conducted by phone to minimize face-to-face contact subjects have with the research team. An encrypted copy of the consent form will be mailed or emailed to subjects prior to the scheduled consent phone call. A study team member will call potential subjects at the scheduled time to review the information in the consent form including study procedures, risks associated with participation, alternatives to participation and whom to contact for additional information. Any questions will be addressed during the course of the phone call and subjects will be encouraged to contact the study team with any questions or concerns they might have at any time. Upon completion of the consent process, subjects will be asked to return a copy of the signed consent form by either scanning the entire document and email back to the study team member or taking a photo of the signature page and emailing a copy to the study team member.

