9.0 DATA AND SAFETY MONITORING

Safety monitoring of research protocols investigating novel PET tracers utilize a combination of tools. These are framed to provide adequate clinical trial oversight ensuring that the research team is complying with the conditions of IRB approval and FDA requirements. The tools enable frequent evaluations of study-related activities, identification of deviations or noncompliance with the conduct of the study or protocol, review of adverse events tracking and reporting, and review of drug production and accountability.

These tools include:

- Study visit checklists – Research Coordinators use study visit checklists to ensure that all study required procedures and processes are met before, during and after the subject has been seen. Items listed on these checklists include informed consent obtained, consent questions answered (and by whom), vitals recorded, medications reviewed, MR safety form, etc. These checklists are reviewed by the study coordinator and are signed off for each study subject by the coordinator monitoring the study to ensure that protocols are followed accurately and include limited variance from protocol.
- Safety monitoring – The safety monitoring of subjects enrolled in the research includes both internal and external safety checks governing the administration of ¹⁸F-DCFPyL. Internal monitoring is performed by co-investigators and external monitoring by a team of four physicians with the appropriate broad clinical and technical. The internal monitoring plan includes a brief review of each subject visit after it occurs. In this regard, the study team will discuss data quality, ¹⁸F-DCFPyL production and administration, and subject compliance and tolerance of research procedures.

The external monitoring plan will be coordinated by the Department of Radiology Medical Imaging Research Support (MIRS) administrative team. MIRS is a working group that provides investigators with the support needed to conduct clinical research that uses imaging as an outcome measure. Members include a core administrative group

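### Women with childbearing capacity who self-report that they are not pregnant are scanned without a pregnancy test, so an unrecognised early pregnancy could be exposed to tracer, CT or gadolinium

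*Combined protocol and SAP*

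**What the plan says.** The synopsis excludes "Women that are pregnant or breast feeding", and the exclusion list in section 4.0 repeats this ("Women that are pregnant or breast-feeding"). Neither place says how or when pregnancy is to be ruled out.

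The only stated method is in section 5.0: "A urine pregnancy test will only be done for women with childbearing capacity that are unable to verify their non-pregnancy status by self-report". This sets two tiers. Self-report comes first, and the urine test is the fallback for women who cannot verify their status that way.

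Four other provisions bear on the question:

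- **MR screening (section 5.0):** "Subjects participating in the PET/MR imaging studies will be screened for contraindications to MRI and MR contrast agents", using a standard institutional form that is not reproduced.
- **Record review (section 5.0):** "Medical records will be reviewed to obtain medical history including physical exams, medications, laboratory tests, imaging results", among other information.
- **Visit checklists (section 9.0):** "Items listed on these checklists include informed consent obtained, consent questions answered (and by whom), vitals recorded, medications reviewed, MR safety form, etc".
- **Withdrawal (section 5.0):** one ground for removing a subject is "Exclusion criteria are discovered after registration but prior to the research examinations".

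**The concern.** The exclusion is absolute, but the check behind it depends on what the woman already knows. A pregnancy in its first weeks may be unknown to her. She can then answer in good faith, meet the rule, and be injected. The word *only* in the rule means that staff who follow the protocol would not test her.

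The possible exposure depends on the group. Every subject receives the tracer. Dosimetry subjects also have two low-dose CT scans, taken to attenuation-correct PET that runs from the top of the skull to mid-thigh and so takes in the pelvis. PET/MR subjects receive gadolinium. Section 6.0 anticipates no immediate benefit to participants, so there is no direct benefit to set against an avoidable exposure. What is at stake is participant safety. The diagnostic-accuracy estimates and the go-forward criteria are unaffected.

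**Working it through.** The plan states no figure for pregnancy risk, so the check has three parts: who can fall into the gap, whether anything else closes it, and how large the exposure is.

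**Who can be affected**

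- Healthy controls: age 18 or over with no upper limit, and surgery still to come ("Scheduled to undergo a hysterectomy and/or salpingo-oophorectomy").
- Cancer patients: surgery may be past or only scheduled, so some are scanned beforehand.
- Dosimetry subjects: their own list in section 4.0 has no surgery item, although they are counted within the 12 controls. The gap is the same whether or not the controls' surgery item applies, because scheduled surgery has not yet taken place.
- Women without childbearing capacity, such as those with a prior hysterectomy, are not affected.

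**Whether another step closes the gap**

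| Provision | Why it does not close the gap |
|---|---|
| MR safety form | Stated only for PET/MR subjects and only for MRI and contrast contraindications. A pregnancy question on it would still be self-report unless it triggered a test. As written, it does not cover a dosimetry subject who has PET/CT alone. |
| Eligibility item requiring no contraindication to MR or PET | Applies to all three groups but names no method of checking. |
| Record review | No pregnancy check named. |
| Visit checklist | No pregnancy item among those listed; the list is open-ended. |
| Withdrawal rule | Acts only once an exclusion has been discovered. |

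**Size of the exposure**

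Inputs, all from section 6.0: effective dose coefficient 0.0165 mSv/MBq; uterus coefficient 1.15E-02 mGy/MBq; highest administered activity 333 MBq (9 mCi); about 10 mSv per low-dose CT, with two scans for dosimetry subjects.

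1. Reproducing the plan's tracer figure: 0.0165 × 333 = 5.49 mSv, which agrees with section 6.0.
2. Tracer dose to the adult uterus: 0.0115 × 333 = 3.83 mGy.
3. Maternal effective dose for a dosimetry subject: 5.49 + 2 × 10 = 25.49 mSv.
4. Ratio to tracer alone: 25.49 / 5.49 = 4.6.

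The figures in steps 1, 3 and 4 are maternal effective doses. Step 2 is the only uterine figure the documents support. They give neither a CT dose to the uterus nor a fetal dose.

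**The case against.** The strongest reply is that this is a considered rule and not an oversight. The protocol excludes pregnancy, asks for verification, and tests when verification fails. To verify could mean more than a bare denial, and the documents do not define it. Every group, dosimetry included, must also be free of contraindications to MR and PET. The MR form and the open-ended checklist may ask about pregnancy, and consent pages are not in the copy reviewed. The affected group is narrow: a woman must be fertile, unknowingly pregnant, and able to satisfy the self-report step. The CT component reaches at most 6 women, the 4.6 ratio does not measure fetal harm, and section 5.0 sets the activity below 9 mCi, so 3.8 mGy is a ceiling. The documents also give no sensitivity for self-report or for the urine test in early pregnancy, so the risk reduction from testing everyone cannot be calculated.

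Much of this stands as a limit on weight. The number at risk is likely small, the ratio describes maternal dose only, and the absence of another check can be asserted only for the visible text. It does not remove the gap. However carefully it is taken, self-report may not show what the woman does not know, and further questions on a form share that weakness. The contraindication criterion names no check. The rule is deliberate, but the documents give no reason for exempting women who self-report.

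**Conclusion.** The concern holds. Followed as written, section 5.0 allows a woman with an unrecognised early pregnancy, who meets an exclusion criterion, to receive tracer together with two CT scans (dosimetry) or gadolinium (PET/MR).

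The supportable exposure figures are up to about 3.8 mGy to the adult uterus from tracer, and a maternal effective dose of 5.49 mSv (tracer alone) or about 25.5 mSv (dosimetry PET/CT). They assume the 333 MBq maximum and the protocol's own dose coefficients and CT estimates. Fetal harm is not quantified. The number of women at risk cannot be estimated, because the documents give no age mix or fertility status.

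The conclusion also assumes that the MR form and the unlisted checklist items contain no mandatory test. The change should be made because the remedy is cheap and the exposure avoidable, not because many cases are expected.

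**What to change.** In section 5.0, remove the self-report exemption. Do the urine test already provided for in every woman with childbearing capacity, and require a negative result on the section 9.0 visit checklist before tracer injection. Women without childbearing capacity, such as those with a prior hysterectomy, need no test.

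The cost is a minor amendment, one checklist line, and a low-cost test taking a few minutes of a 2-3 hour visit. The number of additional women tested is at most 52 and will be lower in practice. A positive result would need follow-up and could postpone a scan.

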| Patient Population | 
1. Adult women with known or suspected gynecological cancers who have had or are scheduled to undergo a hysterectomy and/or salpingo-oophorectomy. N=40
 
2. Normal controls: Women with no imaging evidence of gynecological cancer, who are undergoing hysterectomy and/or salpingo-oophorectomy. N=12 (includes up to 6 Dosimetry subjects)
 
a. Dosimetry : Women with or without suspected gynecological cancer.
 |
| Accrual Objective | 52 women |
| Study Design | Phase 2, single-center, open-label study |
| Study Duration | The estimated accrual period is over 3 years. |
| Primary Objective | 
The purpose of this research is to evaluate whether a novel imaging approach using PSMA-based ¹⁸F-DCFPyL PET and MR imaging can:
 
 1. Document the normal distribution of PSMA in the abdomen and pelvis on PET imaging. 2. Document the normal appearance of the fallopian tubes and ovaries on high resolution MR imaging 3. Accurately determine the presence or absence of cancer 4. Accurately identify the distribution of cancer |
| Specific Aims | 
 1. To establish the biodistribution and radiodosimetry of PSMA-based ¹⁸F-DCFPyL on PET imaging in normal female controls and in females with known or suspected cancer. 2. To determine the ability of PSMA-based ¹⁸F-DCFPyL PET and MR imaging to detect cancer in women with known or suspected gynecologic malignancy and differentiating cancerous tissue from non-cancerous tissue. The performance of PSMA-based ¹⁸F-DCFPyL PET imaging in the detection and localization of cancerous and non-cancerous tissue will be compared to the final surgical pathology reports and to the histological and immunostaining for PSMA positive cancerous tissue on pathology. 3. To determine the most accurate approach in assessing disease burden and location, assessment of tumor burden on both the PSMA-based ¹⁸F-DCFPyL PET and MR imaging together, and then each modality separately will be performed and sensitivity, specificity, and accuracy values will be calculated. |
| Inclusion Criteria | 
 • Women with no imaging evidence of cancer • Women with suspected or documented gynecological cancer and previously underwent or scheduled to undergo a hysterectomy and/or salpingo-oophorectomy • No contraindications for MR or PET imaging. • Greater than or equal to 18 years |

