10.0 STATISTICAL CONSIDERATIONS

The goals of this study are to 1) record the normal distribution of PSMA in the body, 2) record the frequency that the normal fallopian tubes and ovarian are seen on high resolution MR imaging, 3) record the distribution of PSMA in cancer tissue, and 4) estimate the sensitivity, specificity, and accuracy of PSMA PET and MR imaging.

12 healthy controls and 40 subjects with known gynecologic cancer will be enrolled in this pilot study. With final IHC staining as the “gold standard” in detection of cancer, we will estimate the sensitivity, specificity, and accuracy of PSMA PET and MR imaging. The sample size was chosen based on logistical and financial considerations. The table below shows the precision with which we will be able to estimate the sensitivity and specificity of PSMA PET and MR imaging.

| Sensitivity/Specificity | Width of 95% CI |
|-------------------------|-----------------|
| 65% | 31.1% |
| 70% | 29.9% |
| 72.5% | 29.3% |
| 75% | 28.5% |
| 77.5% | 27.7% |
| 80% | 26.5% |
| 82.5% | 25.5% |
| 85% | 24.1% |

Based on this pilot study, we plan to pursue further evaluation in larger, more appropriately powered studies if sensitivity and specificity are at least 80%.

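### Accuracy for the distribution of cancer can be estimated only at resected or sampled sites; imaging-positive sites left in place have no reference, and the net bias for the whole scanned field is of unknown direction

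*Combined protocol and SAP*

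**What the plan says.** **Field and objective.** For the cancer cohort (Section 5.0, Aims 2 and 3), "the whole body (defined in this protocol as base-of-skull to mid-thigh) PET and MR images will be obtained". Item 4 of the primary objective in the synopsis is "Accurately identify the distribution of cancer". Aim 3, in the synopsis and in Section 3.0, calculates sensitivity, specificity and accuracy for tumour burden and its location.

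**Reference.** Section 3.0 names "histologic and immunologic correlation on the pathologic specimens obtained at the time of standard of care surgical resection". Section 10.0 begins its estimation plan "With final IHC staining as the “gold standard” in detection of cancer". The synopsis scores each data point as agreement or disagreement between imaging and IHC. The surgery that makes a woman eligible is hysterectomy, salpingo-oophorectomy or both, either planned or already done (Section 4.0).

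**Matching images to tissue.** Section 5.0 describes two steps. The first starts from pathology: "We will correlate the final surgical pathology report with the images to determine if all sites of disease were seen on PSMA PET and MR". The second starts from the images: "we will identify very specific sites (eg. Left obturator node; Right ovarian mass; etc) for PSMA immunologic staining pre-operatively by review of the imaging", after which the surgeon tries to send those specimens separately.

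**Other information.** The record review in Section 5.0 covers imaging results and anything bearing on "treatment, or outcomes of subjects diagnosis", but no section links it to a reference standard. The only planned study contact after the scan is a telephone call about side effects at 1 to 3 days.

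**Decision rule.** Section 10.0 plans larger studies if sensitivity and specificity both reach 80%.

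**The concern.** The scan covers far more of the body than surgery will remove. If PET or MR is positive at a chest node, the liver, bone or an unsampled retroperitoneal site, and that site stays in place, it yields no pathology or IHC result. The plan gives it no other reference, no indeterminate category and no rule for leaving it out. Following the plan exactly then produces figures that are conditional on resection, for an objective about distribution.

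Two things are lost. False-positive uptake outside resected tissue cannot lower the reported specificity or affect the 80% rule. True disease that imaging found but surgery left behind is not credited to sensitivity. Section 2.0 looks ahead to use in screening and pre-treatment assessment, where performance outside the surgical field matters, so a reader could easily apply a resected-site figure to the whole scan.

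**Working it through.** **1. The plan's own figures.** The Section 10.0 table reproduces. Exact (Clopper-Pearson) 95% intervals with n = 40 have widths of 31.1, 30.0, 29.3, 28.5, 27.6, 26.6, 25.4 and 24.1 points for proportions from 65% to 85%. The table gives 31.1, 29.9, 29.3, 28.5, 27.7, 26.5, 25.5 and 24.1, so the largest difference is 0.1 point. The point therefore does not rest on an arithmetic error. The table makes no allowance for sites without a reference.

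**2. What can be scored.** Both the synopsis and Section 10.0 compare imaging with IHC, which needs tissue. An unresected site has none and drops out by definition. For women operated on before the scan, that earlier specimen cannot verify a site still present at imaging.

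**3. Effect of unresected positives.** Let N resected sites have accuracy A. Add U unresected imaging-positive sites, of which a share f is truly cancer. Accuracy over both sets is (A×N + f×U)/(N + U). Leaving the U sites out overstates accuracy only if f < A.

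The documents give neither U nor f, so these counts are assumed: 100 resected sites, 40 diseased (32 detected, 8 missed) and 60 not (48 true negatives, 12 false positives). All three measures are then 80%. With U = 10:

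| Share truly cancer | Sensitivity | Specificity | Accuracy |
|---|---|---|---|
| 0 | 32/40 = 80.0% | 48/70 = 68.6% | 80/110 = 72.7% |
| 0.5 | 37/45 = 82.2% | 48/65 = 73.8% | 85/110 = 77.3% |
| 1 | 42/50 = 84.0% | 48/60 = 80.0% | 90/110 = 81.8% |

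With U = 20, accuracy is 80/120 = 66.7%, 90/120 = 75.0% and 100/120 = 83.3%.

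**4. Effect of unresected negatives.** The table in step 3 adds positives only. The scan also covers disease-free, imaging-negative regions that nobody resects. With 10 false unresected positives and T unresected true negatives, specificity is (48 + T)/(70 + T):

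- T = 0: 68.6%
- T = 40: 88/110 = 80.0%, the resected-site value
- T = 80: 128/150 = 85.3%, above it

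Unresected disease that imaging missed works against sensitivity. Ten such sites alone give 32/50 = 64.0%.

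**5. Effect of choosing tissue from the images.** Assume true sensitivity and specificity of 80%, 30% of sites diseased, and 90% of imaging-positive but only 30% of imaging-negative sites verified.

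- Observed sensitivity: 0.216/(0.216 + 0.018) = 92.3%
- Observed specificity: 0.168/(0.168 + 0.126) = 57.1%
- Observed accuracy: 0.384/0.528 = 72.7%, against a true 80%

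With the verification rates reversed, the three are 57.1%, 92.3% and 85.7%. Selective verification can therefore push each measure either way.

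**The case against.** The strongest reply is that the plan is open about its tissue reference. Section 2.0 sets the goal as correlating images with staining of resected specimens, and whole body in Section 5.0 describes image acquisition, not the scope of an accuracy claim. A surgical reference is always limited to what is removed. This is also a single-centre pilot with no formal tests, and its go rule leads only to a larger study. That stands as a reason for modest remedies. It does not remove the mismatch, because the objectives and Aim 3 attach accuracy figures to distribution and location without limiting them to resected tissue.

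Three further points need weighing.

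- **False positives can be found in part.** Choosing sites from the images before surgery, with a pelvic node among the examples, can expose false positives beyond the uterus and adnexa. This is correct, but only for tissue the surgeon removes.
- **The unit is unsettled.** The precision table fits n = 40, the number of cancer subjects, which suggests a patient-level analysis. On that reading an extra unresected site in a woman with confirmed cancer may leave the 80% rule unchanged. The synopsis allows for correlated measures within a patient, which points the other way. The effect on the rule is therefore possible, not established.
- **The objective may be narrower.** Section 3.0 refers to "the accurate distribution of cancer and the normal biodistribution of PSMA in the abdomen and pelvis on PET imaging". The anatomical limit reads most naturally with biodistribution. Even if it covers the whole objective, liver and retroperitoneal sites still lack a reference unless resected.

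A reader might infer that the plan intends to exclude unresected sites, or to report the results as whole-body accuracy. The documents say neither. The exclusion follows from the scoring definition, and the text is silent on how the results will be presented.

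**Conclusion.** The concern holds in this form: imaging-positive sites left in place have no reference and cannot enter sensitivity, specificity or accuracy as the plan is written, so those estimates apply to resected or sampled sites only.

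A reader might go further and conclude that accuracy for distribution is overstated. The documents do not support that. With unresected positives alone, overstatement requires the share that is cancer to be below the resected-site accuracy, and nothing in the plan gives that share. On the assumed counts with 10 such sites, accuracy moves from 80% to between 72.7% and 81.8%. Unresected true negatives, unresected missed disease and image-directed sampling add shifts in both directions. A fall in specificity calculated by adding only false positives is built into that formula and is not a finding about this trial. All the site counts and verification rates used here are assumptions that show direction and range; they do not estimate the bias.

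This should be corrected, because the gap affects a stated objective and may affect the 80% rule, and the remedy is cheap. It does not invalidate the pilot.

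**What to change.** 1. In Section 10.0, define the unit and region of analysis. State that sensitivity, specificity and accuracy for distribution, and the 80% rule, refer to resected or sampled sites, and do not present them as results for the whole scanned field.
2. Count and list by region every PET- or MR-positive site that was not resected.
3. As a separate secondary result, classify each listed site as confirmed, refuted or unresolved, using follow-up imaging or later tissue already in the reviewed medical records, over a window fixed in advance.
4. Report the shares confirmed and refuted, with bounds that count the unresolved sites first as all true and then as all false.
5. Do not make the go rule depend on a worst-case specificity built only from unresected positives, since that leaves out unresected true negatives.

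This should be written before results are seen. It needs no new scan, biopsy or reader. The costs are some record abstraction, a narrower conclusion, and some sites that stay unresolved because the records may hold no later imaging or tissue.
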